### 3.2 Primary Study Endpoints

#### Phase I:

The primary end points of Phase I are dose limiting toxicity and maximum tolerated dose. DLT, graded according to the Common Terminology Criteria of Adverse Events (CTCAE) version 4.0, will be defined as one or more of the following events occurring any time during the defined DLT period from initiation of HCQ (Week 0) to 1 month following second TACE (Week 12) excluding the day immediately following TACE: (1) grade 3 or higher hepatobiliary complication, except hepatic pain; (2) grade 4 or higher hepatic pain; (3) grade 3 or higher abnormality of liver function tests including total bilirubin (i.e. >3x the upper limit of normal) and transaminases (i.e. >5x the upper limit of normal, the Hospital of the University of Pennsylvania defines normal transaminases as AST < 41 IU/L and ALT < 63 IU/L); (4) grade 3 or higher elevation of serum creatinine (i.e >3x baseline or >3x upper limit of normal); (5) grade 3 or higher increase in international normalized ratio (i.e. greater than 2.5x upper limit of normal or >2.5x baseline if

CONFIDENTIAL

This material is the property of the University of Pennsylvania. Do not disclose or use except as authorized in writing by the study sponsor

anti-coagulated); or (6) any grade 3 or higher toxicity that is possibly or definitely related to treatment. Given the prevalence of baseline thrombocytopenia in patients with HCC, decreases in platelet count will not be evaluated as a DLT.

Prior investigations have demonstrated the safety of TACE for HCC with a reported rate of major complications related renal dysfunction, biliary injury, gastrointestinal tract ulcer, and treatment related mortality ranging between 2 and 3%(45). Rates of hepatic failure in multiple studies have averaged 7.5%(45).

Phase II:

The primary end point of Phase II will be rate of complete imaging response by mRECIST (see Imaging Assessment of Response under Section 3.3).

### 3.3 Secondary Study Endpoints

Phase I:

Additional secondary endpoints of phase I will include rate of development of any late grade 1 or higher toxicity at any point during combined therapy or during follow up.

Phase II:

The secondary endpoints of the phase II trial will include local tumor control as measured by local progression free survival (LPFS) using mRECIST imaging criteria and overall survival(42,46). For the purposes of the primary and secondary endpoints regarding CR and LPFS, mRECIST will be used. Additionally, during collection of data, imaging response according to EASL guidelines will also be collected. LPFS is defined as time from initiating HCQ therapy (Week 0) to the first diagnosis of local progression of disease, need for TACE of a tumor previously treated with TACE, or death due to any cause. Overall survival is defined as death due to any cause or last patient contact alive.

Table: mRECIST and EASL Imaging Response Assessment

Assessment	Abbreviated Assessment	EASL Definition	mRECIST Definition
Complete Response	CR	100% Decrease in Amount of Enhancing Tissue in Target Lesion	100% Decrease in maximum diameter of Enhancing Tissue in Target Lesion
Partial Response	PR	>50% Decrease in Amount of Enhancing Tissue in Target Lesion	>30% Decrease in maximum diameter of Enhancing Tissue in Target Lesion
Stable Disease	SD	<50% Decrease in Amount of Enhancing Tissue in Target Lesion	<30% Decrease or <20% Increase in maximum diameter of Enhancing Tissue in Target Lesion
Progression of Disease	PD	>25% Increase in Amount of Enhancing Tissue in Target Lesion OR New enhancement in previously	>20% Increase in maximum diameter of Enhancing Tissue in Target Lesion

CONFIDENTIAL

This material is the property of the University of Pennsylvania. Do not disclose or use except as authorized in writing by the study sponsor

		treated lesion warranting further treatment	
--	--	---	--

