### Rationale for TACE to treat HCC

The difference in blood supply to the normal liver parenchyma, dual from the portal vein and hepatic artery, compared to the predominantly hepatic arterial blood supply to HCC, as well as metastatic lesions, allows transarterial chemoembolization (TACE) to be performed with low risk of liver failure or other serious complications(4). TACE is performed by administering high doses of chemotherapeutic agents, most commonly doxorubicin with or without cisplatin and mitomycin-C, into the hepatic artery branches supplying the HCC along with embolic material to slow washout of the chemotherapeutic agents and induce ischemia to the tumor(4). Following chemoembolization, transient elevations in liver function tests (LFTs) can be observed from interruption of hepatic arterial supply to normal parenchyma adjacent to the tumors; however, the majority of studies have shown these effects normalize by one week following therapy without permanent effect(5,6).

Typically, HCC arises in the setting of cirrhosis, and thus orthotopic liver transplant (OLT) is often regarded as the only curative option in patients with localized HCC(3,7). However, the majority of patients with HCC will be outside the criteria for liver transplant to treat HCC and will be of unacceptably high risk for local recurrence or metastatic disease following OLT(3,7). In patients with HCC regardless of stage of disease, TACE has been shown to delay HCC progression, improve local tumor control, and allow downstaging (4,8-11). Two randomized trials demonstrated improved survival among Childs A patients compared to best supportive care(4,12).

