## **4.4 Early Withdrawal of Subjects**

### **4.4.1 When and How to Withdraw Subjects**

- PI Decision: Subjects may be withdrawn at any time during the study if the PI believes it is in the subject's best interest. In this event, the reasons for withdrawal will be documented.
- Subject Participation: Refusal to continue treatment, follow-up, comply with the protocol or withdrawal of consent. In this event, the reasons for withdrawal will be documented.

Patients withdrawing from the study will be entitled to pursue all treatment options available for the treatment of HCC without prejudice from the providing physicians.

Once the subject has discontinued treatment, the primary reason for discontinuing treatment must be clearly documented in the subject's records and on the CRF. The investigator will assess each subject for response at the time of withdrawal.

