### **6.11 Follow-Up Q3 Months:**

Study follow-up of patients will occur at 3 months (+/- 1 week) and 6 months (+/- 1 week) after cessation of HCQ therapy (Week 12 or Week 14). The 3 month and 6 month follow-up visits will include contrast enhanced MRI or CT, laboratory assessments (CBC, PT/INR, CMP) and IR clinical office visits by an interventional radiologist. The follow-up study period will end at 6 months (+/- 1 week) after cessation of HCQ therapy (Week 12) to examine for late toxicity. Patients will continue to be followed beyond the end of follow-up study period per normal Interventional Radiology standard of care and *only* patient data regarding tumor progression and survival will be recorded during this time period to better assess LPFS and overall survival.

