## 7.2 Statistical Methods

Phase I: Frequency of reported side effects and DLTs will be graded according to the Common Terminology Criteria of Adverse Events (CTCAE) version 4.0 and tabled by dose level. Additionally, the timing of these events relative to the first or second TACE will also be tabled by dose level.

Phase II: At the MTD, complete response rate to therapy and 95% confidence intervals will be calculated. Local progression free survival and overall survival curves will be estimated by the Kaplan-Meier method.

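### The LPFS re-treatment event names TACE only, so local failure short of mRECIST progression is scored differently according to the treatment chosen for it

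*Combined protocol and SAP*

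**What the plan says.** Section 3.3 starts the clock at the first HCQ dose: "LPFS is defined as time from initiating HCQ therapy (Week 0) to the first diagnosis of local progression of disease". The three events are, in full, "first diagnosis of local progression of disease, need for TACE of a tumor previously treated with TACE, or death due to any cause". The same section fixes the criteria: "For the purposes of the primary and secondary endpoints regarding CR and LPFS, mRECIST will be used". In the response table there, mRECIST progression is an increase of more than 20% in the enhancing diameter of the target lesion. The EASL column has a second limb for progression, namely fresh enhancement in a treated lesion that calls for more treatment of whatever kind. The mRECIST column has no such limb.

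Section 7.2 gives the whole analysis: "Local progression free survival and overall survival curves will be estimated by the Kaplan-Meier method". Section 7.3 applies intention to treat to primary and secondary endpoints. Neither section says whether anticancer treatment other than TACE is an event, a censoring point or ignored.

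Section 5.6 does not accept other locoregional therapy given concomitantly. Outside that window the protocol foresees other care. Section 6.11 says "Patients will continue to be followed beyond the end of follow-up study period per normal Interventional Radiology standard of care", and only progression and survival data are kept from then on. Section 4.4.1 says "Patients withdrawing from the study will be entitled to pursue all treatment options available for the treatment of HCC".

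The unilobar timeline in Section 3.1 and the Week 10 entry in Section 6.8 both allow a second TACE for tumour with less than a partial response.

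**The concern.** A separate re-treatment event is useful because local control can fail without 20% growth: tumour can remain viable, or start to enhance again, and need treatment. The rule captures that situation for one modality only.

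Take two patients whose treated tumour shows the same residual enhancement, stable by mRECIST, at the same follow-up scan. One needs repeat TACE and has an LPFS event that day. The other has the tumour ablated, radioembolised or resected. Read literally, nothing has happened: the clock runs on, and later scans show the effect of the other treatment. The second patient is scored as still locally controlled by HCQ plus TACE.

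In a single-arm trial, LPFS can only be read against outside TACE experience, and Sections 4.3 and 7.1 say the results will help size larger trials. An endpoint that depends on the clinician's choice of modality is a poor basis for either use. Section 6.11 does not list later treatments among the data kept, so the problem may not be repairable at analysis.

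**Working it through.** The plan states no LPFS rate, median, target or event count, so there is no figure to reproduce. The check is first on the wording, then on size under stated assumptions.

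**Which failures the wording misses**

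| State of a TACE-treated tumour | Next step | LPFS event as written? |
|---|---|---|
| Enhancing diameter up by more than 20% | anything or nothing | Yes, at diagnosis of progression |
| Viable, growth 20% or less | needs TACE | Yes |
| Viable, growth 20% or less | ablation, radioembolisation or resection | No, on a literal reading |
| Less than partial response after first TACE, unilobar | scheduled second TACE | Can be read as yes |

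Row three is the gap. The EASL limb would catch regrowth in that row, but LPFS does not use EASL. The mRECIST threshold is also hard to apply to a complete responder. The enhancing diameter is then zero, a percentage increase from zero is undefined, and the table names no reference scan. Row four acts in the opposite direction. It arises mainly in unilobar disease, since the second session in bilobar disease treats the other lobe.

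**Size of row three, with death competing**

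Assumed inputs, none from the documents: exponential local failure with median 8 months; exponential death with median 24 months; a share *a* of failures falls in row three, and each then waits a further exponential time with the same 8-month median before it is counted.

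- With every failure counted: S(12) = 2^(−12/8) × 2^(−12/24) = 2^(−2) = 25.0%. The median is 6.0 months, because 1/8 + 1/24 = 1/6.
- As written: S(12) = 0.25 × (1 + *a* × 1.5 ln 2), with 1.5 ln 2 = 1.04.
- *a* = 0: 25.0%, median 6.0 months.
- *a* = 10%: 27.6%, median 6.5 months.
- *a* = 20%: 30.2%, median 7.0 months.
- *a* = 30%: 32.8%, median 7.6 months.

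**Sensitivity to the assumed level**

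Let S be 12-month LPFS with every failure counted, and *f* the share of all first events that fall in row three. If these are never counted within 12 months, the reported value is S + *f*(1 − S). If they are counted after a second wait with the same hazard, it is S(1 − *f* ln S). At *f* = 30%:

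| S | Never counted | Counted later |
|---|---|---|
| 30% | 51% | 40.8% |
| 50% | 65% | 60.4% |
| 70% | 79% | 77.5% |

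At *f* = 0 nothing changes.

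**Row four, the opposite direction**

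If a share *q* of patients has the scheduled second TACE to the same tumour and this is scored as an event, 12-month LPFS becomes S(1 − *q*). With S = 25%, *q* = 10% gives 22.5% and *q* = 20% gives 20.0%. If both effects act independently at 20%, the result is 30.2% × 0.8 = 24.2%, close to the 25.0% obtained with neither. With *a* = 30% and *q* = 10% it is 32.8% × 0.9 = 29.5%. With *a* = 10% and *q* = 20% it is 27.6% × 0.8 = 22.1%. The sign depends on two shares that the documents do not give.

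**The case against.** The strongest reply is that local progression is an event in its own right, with no condition on what follows. This stands. A reader might infer that any local failure treated by something other than TACE escapes LPFS. The text does not support that: only failure short of mRECIST progression can escape, and it may still be counted later as progression or death.

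Second, the event is a need for TACE, not its receipt, so a tumour judged to need TACE but treated otherwise could be scored. That reading is possible. It makes the rule ambiguous, however, and two analysts could score one record differently.

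Third, exposure is limited. Other locoregional therapy is not accepted concomitantly, the disease is unresectable, and patients are not transplant candidates at entry (Section 4.1). What remains is mainly care after the 6-month visit or after withdrawal. This bounds the problem, but those are periods in which LPFS events are still collected.

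Fourth, transplant or systemic therapy without progression is not obviously a local failure. The background says "TACE has been shown to delay HCC progression, improve local tumor control, and allow downstaging", but that is general and does not predict how often this cohort would reach transplant. Counting, censoring or ignoring these treatments is an estimand choice. Following patients regardless of later therapy fits the intention-to-treat statement, and censoring at systemic therapy may itself be informative. This objection stands, so the point requires the choice to be stated in advance, not a particular answer.

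Finally, LPFS has no test, target or decision rule. This also stands and limits the consequence.

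**Conclusion.** The rule should be corrected, within limits. Residual or recurrent viable tumour below the mRECIST progression threshold is an LPFS event if it needs TACE and, read literally, is not one if another local treatment is used. For those patients this component lengthens LPFS. Under the assumed 8-month failure and 24-month survival medians, with 0 to 30% of failures affected, a 12-month LPFS of 25% would read as 25% to 33%. The shares and medians are assumptions, and the true size is unknown.

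A reader might go on to conclude that the reported LPFS will be overstated. The documents do not show this. They give no frequency of non-TACE treatment, and the same phrase can count the planned second TACE as an event, which shortens LPFS. The net direction is unknown.

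The primary complete-response test, the sample size and the stage-one stopping rule are unaffected.

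**What to change.** - **Section 3.3:** replace the second LPFS event with: need for any further locoregional treatment or resection directed at a tumour that has had TACE on study, other than the protocol-scheduled second TACE session. The exclusion matters, since without it a broader event would still count the planned session. Sections 3.1 (Week 8) and 6.8 (Week 10) time that session differently for unilobar disease and must be reconciled so that the exclusion can be applied.
- **Section 6.11:** add the date and type of any subsequent HCC treatment to the data kept after the follow-up period.
- **Section 7.2:** state in advance whether transplant and systemic therapy without prior progression are ignored, censored or counted as events, and run the alternative as a sensitivity analysis.

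The cost is about one sentence in each section and one case report form field, with no added patients or procedures. The downside is that the LPFS estimate may become somewhat less favourable.

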**Timeline Unilobar HCC**

For patients with unilobar HCC, duration of HCQ therapy, frequency/timing of laboratory assessments, and definition of DLTs will be the same as with bilobar HCC. However, imaging, response assessment to initial TACE and phone call or clinical office visit following initial TACE will be performed at calendar Week 7. Repeat chemo-embolization may be performed at calendar Week 8 on HCCs with less than PR by mRECIST (see Imaging Assessment of Response under Section 3.3) or new HCCs which have developed since the initial TACE so long as LFTs are below the threshold of dose limiting toxicity. Subsequent follow-up clinic visits and imaging will be the same as with bilobar HCC - 3 months (+/- 1 week) and 6 months (+/- 1 week) following the last clinic visit.

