## **6 Study Procedures**

*Please Note - All visits will be by calendar week. All visits from Weeks 0 to 14 will have a grace period of 14 days/2 weeks to allow for scheduling of procedures, weekends, holidays as well as off service days for the interventionalist while not exceeding a total of 15 weeks total time taking HCQ. In addition, all study visits/events are sequential so that a patient cannot proceed to a study visit without completing the prior visit (e.g. Week 2 visit events must be completed before the Week 3 visit, Weeks 3 visit events must be completed before Week 4 visit, etc.).*

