### **6.7 Week 8:**

Patients with **bilobar disease** will undergo TACE of the contra-lateral lobe to treat additional HCC. This second session of TACE will be performed only if the patient's clinical status and laboratory assessments have returned to baseline and the patient has not had any dose limiting toxicity.

Patients with **unilobar disease** will undergo an IR clinical office visit. At the clinical office visit - compliance with HCQ therapy, toxicity and AEs will be recorded. In order to determine if a second session of TACE is needed for subjects, a response assessment with imaging (contrast enhanced MRI or CT) will also be conducted at this visit.

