### **6.8 Week 10:**

Patients with **bilobar disease** and patients with **unilobar disease not undergoing a second session of TACE** will have laboratory assessments (CBC, PT/INR, CMP) to check for DLT.

Other patients with **unilobar disease** will undergo second session of TACE. This second session of TACE will be performed only if 1.) the HCC is less than PR by mRECIST or new HCC has developed since the initial TACE, 2.) the patient's clinical status and laboratory assessments have returned to baseline and 3.) the patient has not had any dose limiting toxicity.

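### The LPFS definition has no exception for the protocol's own conditional second TACE, so a unilobar patient retreated for stable disease counts as an early LPFS event without mRECIST progression

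*Combined protocol and SAP*

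**What the plan says.** Section 3.3 makes LPFS a Phase II secondary endpoint. The clock starts with HCQ at Week 0 and stops at the first of three things: local progression, "need for TACE of a tumor previously treated with TACE, or death due to any cause". The same section says: "For the purposes of the primary and secondary endpoints regarding CR and LPFS, mRECIST will be used". Its response table defines stable disease as "<30% Decrease or <20% Increase in maximum diameter of Enhancing Tissue in Target Lesion", and progression as an increase of more than 20%.

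The treatment schedule builds a conditional second session into unilobar disease:

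- Section 3.1, Timeline Unilobar HCC, images the patient at Week 7 and then says: "Repeat chemo-embolization may be performed at calendar Week 8 on HCCs with less than PR by mRECIST". It also allows treatment of new tumours.
- Section 6.7 places that imaging at Week 8 and gives its purpose: "In order to determine if a second session of TACE is needed for subjects".
- Section 6.8 places the second session at Week 10, if "the HCC is less than PR by mRECIST or new HCC has developed since the initial TACE". It also requires that clinical status and "laboratory assessments have returned to baseline and 3.) the patient has not had any dose limiting toxicity".
- Section 6 adds: "All visits from Weeks 0 to 14 will have a grace period of 14 days/2 weeks".
- Section 6.10 schedules imaging and response assessment at Week 14 for unilobar patients who had the second session.

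Section 7.2 plans a Kaplan-Meier curve for LPFS and nothing further. Section 7.3 specifies intention to treat. None of sections 6.11, 7.2 and 7.3 exempts the second session or gives a censoring rule for it.

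**The concern.** Less than partial response covers stable disease as well as progression. A unilobar tumour that shrinks, but not by enough, can therefore be retreated as the protocol foresees. The LPFS definition then scores that retreatment, or the judgement that it is needed, as loss of local control.

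Elsewhere the protocol handles the second session as part of the treatment course. The DLT window in sections 3.1 and 3.2 runs to about a month after it. Section 7.2 tabulates toxicity by its timing relative to the first or second TACE. Section 6.10 assesses response after it. Section 7.1 cites complete response rates after repeated TACE, including a series in which the rate rose from 14% to 38% after a second session.

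At stake is what the LPFS curve means. Its early part would mix true local failure with completion of the planned course. Two analysts could also draw different curves from the same data, depending on whether they read the definition literally or assumed an unwritten exception.

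**Working it through.** The documents give no LPFS rate, median or event count, so there is no stated figure to reproduce. The check traces one patient through the text and then sizes one event.

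**Trace (unilobar, illustrative tumour sizes)**

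1. Week 0: HCQ starts and the LPFS clock starts (3.3).
2. Week 4: first TACE (6.4).
3. Week 7 (3.1) or Week 8 (6.7): imaging. Suppose the enhancing diameter falls from 5.0 to 3.6 cm. Decrease = (5.0 − 3.6)/5.0 = 28%. This is below 30%, so the tumour is stable disease: not partial response and not progression.
4. The tumour meets the below-PR criterion in 3.1 and 6.8. If the other conditions hold, it is treated again at Week 8 (3.1) or Week 10 (6.8).
5. Under 3.3 this is need for TACE of a treated tumour. The event falls between nominal Week 7, if dated to the imaging, and nominal Week 10, if dated to the session. With the 14-day window the latest date is about Week 10 + 2 = Week 12.
6. Week 14: response is assessed after the second session (6.10) and can be complete. On nominal dates the LPFS event precedes this by 14 − 10 = 4 to 14 − 7 = 7 weeks.

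**Who is and is not added by the literal reading**

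- Unilobar, stable disease, retreated: added.
- Unilobar, stable disease, session judged needed but withheld for laboratory values or DLT: the event is need, not delivery, so literally also added.
- Unilobar, progression at the same imaging: an event under any reading, so not added.
- Second session only for new tumours: no treated tumour is involved, so not added.
- Bilobar, contralateral session at Week 8: it treats additional tumour in the other lobe (6.7), so not added. The retreatment rule applies equally to bilobar tumours, but their first scheduled post-TACE imaging is at Week 12 (6.9).

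**Size of one event**

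With no earlier events or censoring, S(t) = 1 − d/n. The sizes n = 46 (full Phase II) and n = 16 (stop after stage 1) come from section 7.1.

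- d = 1, n = 46: 1/46 = 2.2 points.
- d = 1, n = 16: 1/16 = 6.3 points.

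The effect of each patient lasts only until that patient would otherwise have had an event.

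**Scale under assumed shares**

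The documents give neither the share of unilobar patients nor the share of those with stable disease who are retreated or judged to need it. Purely as an assumption, take 30–70% for the first and 10–40% for the second:

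- Low: 0.30 × 0.10 = 0.03; × 46 = 1.4 patients, 3 points.
- High: 0.70 × 0.40 = 0.28; × 46 = 12.9 patients, 28 points.

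This range shows only that the answer depends on figures the documents do not contain. It is not an estimate.

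**The case against.** The strongest reply is that the component works as designed. Need for retreatment adds something to progression only if it can occur without progression. Counting a tumour still below partial response after TACE as failed local control is coherent. This stands: the component is a legitimate choice, and an event without progression is not in itself a contradiction. A reader might infer that the sentence assigning mRECIST to LPFS rules such events out. It does not, because it governs how imaging is read and leaves the listed components in place. What remains is that the component, as written, also captures a step of the planned course, and no text says this was intended.

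A reader might also infer that LPFS contradicts the primary endpoint. The documents do not go that far. Section 3.2 names no assessment time for complete response, so it is an inference that the Week 14 assessment decides the primary result. An early time-to-event failure followed by a complete response is not illogical either, since the two measure different things. The series cited in 7.1 makes complete response after a second session foreseeable, but the documents do not say how many of those patients had stable disease beforehand.

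Nor does every unilobar patient with stable disease become an event through retreatment. Section 3.1 is permissive, and section 6.8 adds laboratory, clinical and DLT conditions.

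Finally, the effect is unquantified and confined to a descriptive secondary endpoint. That is correct and limits the weight of the point. It does not remove it, because the remedy needs only wording and data already collected.

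**Conclusion.** The point holds as a defect in the LPFS definition that should be corrected. Followed literally, section 3.3 makes the protocol's conditional second session in unilobar stable disease an LPFS event at about nominal Week 7 to 10 without mRECIST progression. Each affected patient costs 2.2 points of the early curve at n = 46, or 6.3 points at n = 16, assuming no earlier events or censoring. The number affected cannot be derived.

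It would be too strong to say that the LPFS curve is known to be seriously biased: the documents contain no figures to show that. It would also be wrong to carry the point to the efficacy decision. The Simon rule counts complete responses only and does not use LPFS.

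**What to change.** In 3.3, state that:

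- local progression by mRECIST and death from any cause count at any time from Week 0;
- need for TACE of a previously treated tumour counts only when identified at or after the end-of-course assessment, meaning Week 12, or Week 14 after a unilobar second session.

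The conditional second session is then not by itself an event, whether given or withheld, and a need that persists after the course is. Unilobar patients without a second session have only a telephone contact at Week 12 (6.9). The text should therefore make clear that, for them, Week 12 is the date from which a need counts; their next scheduled imaging is the 3-month visit.

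In 7.2, add LPFS under the current literal definition as a sensitivity analysis.

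Separately, the timing of the unilobar assessment and second session (Weeks 7 and 8 in 3.1; Weeks 8 and 10 in 6.7 and 6.8) must be reconciled. It also sets the event date under the literal definition.

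The cost is a few sentences in 3.3 and one line in 7.2. No new data are needed, because the imaging and the second session are already study procedures. There are two downsides. Early retreatment for stable disease no longer counts as failure in the main curve. A unilobar tumour may also receive two sessions before retreatment counts, against one per lobe in bilobar disease. The sensitivity curve shows the effect. The change should be made before LPFS is analysed, so that the definition is not chosen with the data in view.
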